### 11.2 DISPOSITION OF PATIENTS

Disposition of patients will be depicted for patient status and patient analysis populations. The total number of patients for each of the following categories will be described:

- Enrolled patients
- Patients failed to be enrolled and the reason for non-enrollment
- Safety population
- ITT population
- Per-Protocol population.

## **11.3 ANALYSIS POPULATIONS**

### **11.3.1 Intent-to-treat population**

Intent-to-treat (ITT) population: all patients who met all the eligibility criteria and who are actually treated.

### **11.3.2 Safety population**

Safety population: all patients who have signed the Informed Consent Form (ICF) and have been exposed to at least one dose or part of a dose of IMP.

### **11.3.3 Per-protocol population**

Per-protocol population: patients of ITT population without major protocol deviations. Major deviations will be defined in the statistical analyses plan before database frozen.

## **11.4 STATISTICAL METHODS**

### **11.4.1 Extent of study treatment exposure and compliance**

The extent of study treatment exposure and compliance will be assessed and summarized within the safety population.

#### ***11.4.1.1 Extent of investigational medicinal product exposure***

The duration of IMP exposure is defined as follows last dose date – first dose date + 14 days regardless of unplanned intermittent discontinuations.

The IMP dose as well as temporary and permanent discontinuations of the IMP will be described (with reasons).

#### ***11.4.1.2 Demographic and baseline characteristics***

All demographic and baseline characteristics will be summarized in the ITT population using descriptive statistics.

#### ***11.4.1.3 Compliance***

A given administration will be considered non-compliant if the patient did not take the planned dose of treatment as required by the protocol. No imputation will be made for patients with missing or incomplete data.

Treatment compliance, above-planned and under-planned dosing percentages will be summarized descriptively (N, mean, SD, median, min, and max). The percentage of patients with compliance <80% will be summarized.

#### **11.4.1.4 Prior and concomitant treatments**

The prior and concomitant medications will be presented for the Safety population. Medications will be summarized according to the WHO-DD dictionary, considering the first digit of the ATC class (anatomic category) and the first three digits of the ATC class (therapeutic category). All ATC codes corresponding to a medication will be summarized. Patients will be counted once in each ATC categories (anatomic or therapeutic) linked to the medication, therefore patients may be counted several time for the same medication. The table for prior and concomitant medications will be sorted by decreasing frequency of anatomic category followed by all other therapeutic classes. In case of equal frequency regarding anatomic categories, alphabetical order will be used.

#### **11.4.2 Analyses of efficacy endpoints**

##### **11.4.2.1 Analysis of primary efficacy endpoint**

The primary study objective is to assess the change in RAID score from baseline to W24. The number of available data, mean, standard deviation, median and range (minimum, maximum) will be provided with the 95% confidence interval of mean change from baseline to W24. Main analysis will be done on ITT population. Sensitivity analysis will be conducted in reproducing the same analysis using the per-protocol population.

In addition, multivariate analyses such as ANCOVA (Analyze of Covariance), Logistic Regression and Multiple Correspondences analysis can be performed from baseline in order to exploratory explain different profiles of patients. The details of these analyses will be described on the statistical analyses plan before database frozen.

In case of any event mentioned below, the last available endpoint before the considered event will be taken in account (for RAID score for primary endpoint and for all other secondary endpoints):

- Lack of efficacy
  - More than one glucocorticoid infiltration per articulation
  - Dose increase of an ongoing glucocorticoid or start of systemic glucocorticoid treatment
  - Change in NSAID due to lack of efficacy or adverse event considered as related to treatment by the investigator
- Missing data
  - Treatment discontinuation due to lack of efficacy or adverse event (except for AEs due to NSAID). For all other cases, missing data will not be replaced.

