### 8.8.2 Permitted medications

**DMARDs:** Treatment with csDMARDs (azathioprine, chloroquine, hydroxychloroquine, leflunomide, MTX, sulfasalazine), at a stable dose initiated at least 4 weeks prior to Baseline, is permitted during the study. If applicable, DMARDs can be used alone or in combination except for the combination of MTX and leflunomide. If applicable, patients should remain on the same background csDMARD(s) throughout the study.

The dose and route of administration of csDMARDs at entry in the study should be continued without change during the study period unless an adjustment is necessary for safety reasons. All biologic DMARDs are prohibited during the study and must be discontinued and washed out prior to the initiation of study treatment. The use of prohibited medications will require the patients to be withdrawn from the study.

**Folic Acid:** In order to minimize MTX toxicity, all patients treated with MTX will receive folic acid or equivalent at a dose of at least 5 mg/week. This can either be given as a single weekly dose usually 48 hours after MTX administration or be divided into daily doses to achieve at least 5 mg folic acid per week. It is the Investigator's decision as to which dosing regimen is used.

**Oral corticosteroids:** Patients may receive oral corticosteroids at dose of  $\leq 15$  mg/day prednisone or equivalent during the study, if initiated at least 4 weeks prior to Baseline. To treat AE for a condition not related to RA that requires a corticosteroid dose modification, increased doses of oral corticosteroids during the study will be permitted.

Corticosteroids can be stepwise discontinued at the investigator's discretion in eligible patients in order to achieve a steroid-free condition. After a potential increased dose of oral corticosteroids, up to 15 mg of prednisone daily (or equivalent), the corticosteroid dose should be tapered down to the previous level as rapidly as medically possible. In cases where increased corticosteroids doses for RA conditions can't be tapered down during the study, patient maintenance in the study should be reevaluated based on the investigator's judgment.

Intranasal, inhaled, or topical corticosteroids as per label are permitted, as needed throughout the course of the study.

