1.6. MODIFICATIONS FROM THE PROTOCOL

Analysis sets definition have been reviewed:

Population	Protocol definition	Statistical analysis plan definition
Enrolled patients	No definition	All patients screened, who have signed the Informed Consent Form (ICF) and who never took the study treatment at any time before baseline.
Intent-to-treat (ITT) population	All patients who met all the eligibility criteria and who are actually treated.	All patients included (i.e. for whom the inclusion decision "Has the decision to include the patient been taken" is 'Yes') and who took the treatment at least once
Per-protocol population	Patients of ITT population without major protocol deviations. Major deviations will be defined in the statistical analyses plan before database frozen.	Patients of ITT population without major protocol deviations as defined during the Data Review meeting and who are evaluable for the main criterion

Data will be presented according to a subgroup not defined in the protocol. This subgroup has 3 categories^{DD}:

- Patients treated with csDMARDs for whom Sarilumab is prescribed in addition to csDMARDs at baseline.
- Patients treated with biological therapy for whom Sarilumab is prescribed in addition to csDMARDs at baseline.
- Patients previously treated with csDMARDs or biological therapy for whom only Sarilumab in monotherapy is prescribed at baseline.

Also, an analysis has been performed with all screened patients who have met all the eligibility criteria and who have received the treatment at baseline visit (D1). Only data from the baseline visit have been analysed.

In the protocol section 11.4.1.3, compliance should be evaluated according to the planned dose required by the protocol. No planned dose is required by the protocol. Hence, compliance will be evaluated according to the number of injections during the study (see section 5.1.4).

Adverse events will not be described by SOC, HLG, HLT and PT but only by SOC and PT.

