6.4. MISSING DATA

For the primary endpoint, in case of treatment discontinuation due to lack of efficacy (as defined in Protocol Version 2 section 11.4.2.1) or adverse event (except for AEs due to NSAID), the last available endpoint before the considered event will be taken in account (for [RAID](#) score for primary endpoint and for all other secondary endpoints). For all other cases, missing data will not be replaced.

MISSING OR INCOMPLETE DATES

For all dates (except adverse events and concomitant treatments):

- If only day is missing, it will be replaced by '15'
- If day and month are missing, day will be replaced by 1 and month will be replaced by July '7'
- In case of missing year or complete missing date, no replacement will be performed

For dates relative to adverse events (AE) and concomitant treatments, if a date is completely or partially missing, date will not be replaced but:

- If day is missing and start date/end date of AE/treatment occurred before or the same month as the end of study, AE/treatment will be considered as "treatment-emergent" by default.
- If day and month are missing and start date/end date of AE/treatment occurred the same year as the end of study, AE/treatment will be considered as "treatment-emergent" by default.
- In case of missing year or complete missing date, start date/end date of AE/treatment will be considered as "treatment-emergent" by default.

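### Protocol 11.4.2.1 carries the last value forward after any listed rescue event; SAP 6.4 does so only when treatment is discontinued, and SAP 1.6 does not list the change

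*Protocol*

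**What the plan says.** Protocol 11.4.2.1 sets the data-handling rule for the primary endpoint and extends it to all secondary endpoints: "In case of any event mentioned below, the last available endpoint before the considered event will be taken in account". The events come in two groups. The first, labelled as lack of efficacy, contains "More than one glucocorticoid infiltration per articulation", "Dose increase of an ongoing glucocorticoid or start of systemic glucocorticoid treatment", and a change of NSAID for inefficacy or for a related adverse event. The second, labelled as missing data, contains discontinuation of treatment for inefficacy or an adverse event.

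SAP 6.4 covers the same endpoints. It uses the earlier value "in case of treatment discontinuation due to lack of efficacy (as defined in Protocol Version 2 section 11.4.2.1) or adverse event" and then adds: "For all other cases, missing data will not be replaced".

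SAP 1.6 records departures from the protocol. It begins with "Analysis sets definition have been reviewed" and goes on to a new subgroup, an analysis of baseline data, the compliance definition and the coding levels for adverse events. It does not mention the carry-forward rule. SAP 1.7, on changes since the first approved SAP, does not mention it either.

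**The concern.** In the protocol, the steroid, infiltration and NSAID events each trigger the rule. In the SAP they only define one reason for stopping treatment, and it is the stopping that triggers the rule. The SAP therefore does not implement the section it cites, and nothing tells the reader whether this was a decision or a drafting slip.

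The rule decides which week-24 values enter the analysis. In a single-arm descriptive trial, the mean RAID change with its confidence interval is the whole primary result. No test is affected, because Protocol 11.4.2.3 states that there are none. What can change is the reported mean change, the other efficacy summaries, and the low-disease-activity and remission rates. The difference is also one of interpretation: one rule removes values obtained after rescue treatment and the other keeps them.

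**Working it through.** **Step 1. The two rules side by side.**

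| Patient | Protocol 11.4.2.1 | SAP 6.4 |
|---|---|---|
| Stops sarilumab at week 14 for inefficacy | week-12 value | week-12 value |
| Oral steroid increased for RA at week 14, tapered, stays on sarilumab, attends week 24 | week-12 value | observed week-24 value |
| NSAID changed for inefficacy at week 14, stays on sarilumab, attends week 24 | week-12 value | observed week-24 value |
| Oral steroid increased at week 3 for a condition other than RA, stays on sarilumab, attends week 24 | baseline value, so change = 0 | observed week-24 value |

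The rules agree in the first row and differ in the other three. The last row matters for the fix: the protocol event as worded has no limit on the reason for the increase.

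**Step 2. Can such patients occur?** Yes. Protocol 8.8.2 permits oral steroid increases for adverse events unrelated to RA. After an increase, it says that "the corticosteroid dose should be tapered down to the previous level as rapidly as medically possible". It reconsiders study participation only if an increase for RA cannot be tapered. The mandatory stopping list in 10.3.3 names other biologic DMARDs but neither glucocorticoids nor NSAIDs.

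**Step 3. The plan's own precision.** Inputs from Protocol 11.1: SD 2.5, 122 evaluable patients, two-sided 95% interval.

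- 1.96 × 2.5 / √122 = 0.44, as stated.
- With the 112 evaluable patients of the protocol summary: 1.96 × 2.5 / √112 = 0.46.

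The 122 versus 112 mismatch is a separate matter; both are used here only as a yardstick.

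**Step 4. Scale, by assumption only.** Let p be the share of patients with a listed event who stay on sarilumab and have a week-24 RAID. Let d be the average signed difference between the two candidate values in those patients. The two means differ by p × d. Neither p nor d is in the documents.

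| p | abs(d) = 0.5 | abs(d) = 1 | abs(d) = 2 |
|---|---|---|---|
| 1% | 0.005 | 0.01 | 0.02 |
| 5% | 0.025 | 0.05 | 0.10 |
| 10% | 0.05 | 0.10 | 0.20 |
| 20% | 0.10 | 0.20 | 0.40 |

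Because d is an average of signed differences, it can be near zero if some patients improve after the event and others worsen. The range therefore starts at 0. Its top, 0.40, is about 90% of 0.44, but needs 20% affected with an average net difference of 2 points.

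Read the other way, a shift of 0.1 in the mean needs 0.1 × 122 = 12.2 points in total. That is about 6 patients at 2 points each, 12 at 1 point or 24 at 0.5 points.

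For a response rate, each reclassified patient moves the rate by 1/122 = 0.8 to 1/112 = 0.9 percentage points.

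These figures are for the simple mean change. The repeated-measures model in SAP 5.3.2.2 takes the same visit-level changes as its response, so the choice of rule enters there too, though the shift need not be identical.

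**The case against.** The strongest reply is that a rule is in writing. SAP 6.4 is explicit, it cites 11.4.2.1, and it can be read as using the first group of events to define the inefficacy named in the discontinuation item. On that view the defect is one missing row in SAP 1.6. Part of this stands: the SAP is not silent, and its authors may have believed they were restating the protocol. But the protocol's opening sentence applies to every event listed, and discontinuation is a separate item. If each event required stopping, listing the steroid and NSAID events as triggers would add nothing.

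A second reply is that keeping observed values after rescue is a legitimate choice. That also stands, which is why the fix offers it, provided that it is declared.

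A third is that the per-protocol analysis deals with rescue. It does so only in part: a steroid increase that 8.8.2 permits need not be a deviation at all, and major deviations are settled at the data review meeting.

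A reader might go further and infer that the SAP rule flatters sarilumab, or that the protocol rule understates it. The documents support neither. A patient still improving does better on the observed value; one who flared may do worse. Any one-directional figure depends on an assumed course of response.

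A reader might also make much of the injection count. Protocol 8.8.1 limits intra-articular injections without a per-joint unit, while 11.4.2.1 counts them per joint. But one governs permitted treatment and the other data handling, so they need not share a unit. For patients who stay on treatment, the difference matters only if the event triggers are kept. It is a minor alignment point.

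**Conclusion.** The inconsistency is real and can be established from the text alone. For patients who have a listed steroid, infiltration or NSAID event, remain on sarilumab and have a week-24 value, the protocol and the SAP select different values for the primary and all secondary efficacy endpoints, and the SAP does not say that it departs from the protocol.

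The size is not derivable. Under the assumptions in the working it runs from nothing to 0.40 points on the mean RAID change, the upper end being an extreme case. No direction is claimed. The documents do not show that the change was made with knowledge of results, and that should not be inferred from its absence in SAP 1.6. The point should be corrected because the remedy is cheap and the rule selects the primary-endpoint values.

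**What to change.** Rewrite SAP 6.4 along these lines: for the primary and secondary efficacy endpoints, the last value before the event is used (a) after any lack-of-efficacy event in Protocol 11.4.2.1, whether or not sarilumab is stopped, and (b) after discontinuation for inefficacy or an adverse event, as now. For (a), the glucocorticoid event is limited to a systemic start or increase made for RA; increases for other conditions, which 8.8.2 permits, do not count. Report the same analyses on observed values as a sensitivity analysis. List the limit to systemic changes for RA in SAP 1.6, since it narrows 11.4.2.1. If the triggers are kept, also state there whether infiltrations are counted per joint or per patient.

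If the sponsor intends the discontinuation-only rule, state it in SAP 6.4 as the primary rule, list it in SAP 1.6 as a change from 11.4.2.1, and report the protocol rule as the sensitivity analysis.

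The cost is a few sentences in SAP 6.4, an entry in SAP 1.6, a second run of the efficacy tables, and a check of route and reason for steroid changes at data review. Protocol 8.8 already requires the type of drug, the amount and the reason to be recorded. The downside of the first option is that a few observed week-24 values are replaced by earlier ones; the sensitivity analysis shows how much that matters.

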##### **11.4.2.2 Secondary analyses**

All secondary parameters will be described. For continuous variables, the number of available data, mean, standard deviation, median and range (minimum, maximum) will be provided. Categorical variables will be summarized using number and percentage of patients. Patients with missing data will not be included in the calculation of percentages. 95% CI will be provided.

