
STATISTICAL CONSIDERATIONS
	
Sample size determination:
 
According to the literature and previous studies having assessed sarilumab, the standard deviation (SD) of the RAID score could be estimated at 2.5 points. On this basis, a sample size of 140 included patients in order to have at least 112 evaluable patients (assuming almost 20% of non-evaluable patients), produces a precision, two-sided 95% confidence interval (CI), with a distance from the mean to the limits that will be less than 0.5 (considering 20% non-evaluable patients) when the estimated SD is 2.5, assuming that the change from baseline will be from 30% to 50% of baseline score.
 
Analysis populations:
 
 
• Intent-to-treat (ITT) population: all patients who met the eligibility criteria and who are actually treated.
 
• Safety population: all patients who have signed the Informed Consent Form (ICF) and have been exposed to at least one dose or part of a dose of IMP.
 
• Per-protocol population: patients of ITT population without major protocol deviations.
 
 
Primary analysis:
 
The primary study objective is to assess the change in RAID score from baseline to W24.
 
The number of available data, mean, standard deviation, median and range (minimum, maximum) will be provided with the 95% confidence interval of the mean change from baseline to W24. Main analysis will be performed on ITT population. Sensitivity analysis will be conducted in reproducing the same analysis using the per-protocol population.
 
In addition, multivariate analyses such as ANCOVA, Logistic Regressions and Multiple Correspondences analysis can be performed from baseline in order to exploratory explain patient profiles.
 
Analysis of secondary endpoints:
 
All secondary parameters will be described; 95% CI will be provided.

DURATION OF STUDY PERIOD (per patient)	The total duration of the core study period per patient is expected to be approximately 32 weeks: 

• Up to 4-week screening

• 24 weeks treatment

• 2-4 week post-treatment observations.

 For patients who will enter in the LTE period, a maximum of another 24 weeks is planned.
---	--

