3. GENERAL STATISTICAL APPROACH

3.1. DESCRIPTIVE STATISTICS

Each modality of qualitative data will be presented with their number, percentage and 95% CI will also be presented.

For quantitative data, mean, median, minimum and maximum as well as standard deviation , interquartile range and 95% CI will be described.

For all the variables, number of available and missing observations will be specified.

Data will be presented using an appropriate number of decimal places (i.e. the number of decimal places used does not imply undue precision):

- Raw data : same number of decimal as collected,
- Derived data: The appropriate number of decimal places will be determined by general practice, mathematical rationale or scientific rationale (e.g. age should be presented in whole numbers),
- Mean, median and standard deviation : reported to one decimal place greater than the raw/derived data that they summarise,
- Minimum and maximum : same precision as the raw data,
- Percentage : one decimal place,
- P-values : four decimal places (e.g.: $p=0.0037$), after rounding. P-values which are less than 0.0001 will be presented as '<0.0001'.

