5.3. STATISTICAL METHODS

5.3.1. Disposition of patients

Key information of the study will be presented (First patient first visit, last patient last visit, first patient last visit, last patient last visit, number of centers with at least one patient included, enrollment duration (months)^{DD}).

Disposition of patients will be depicted for patient status and patient analysis populations. The total number of patients for each of the following categories will be described:

- Enrolled patients

- Patients failed to be enrolled and the reason for non-enrollment
- Safety population
- ITT population
- Per-Protocol population.

Summary tables and flowcharts will present the number and percentage of subjects who not entered in the study and reason for non-enrolment into the registry will be presented overall (non-compliance with inclusion / exclusion criteria, patient's refusal of consent).

Summary tables and flowcharts will present the number of subjects at each assessment and the number of subjects by population. Follow-up duration^{DD} (weeks) will be calculated overall. The number and percentage of subjects who withdrew from the study and the reasons for premature withdrawal will be presented overall (adverse event, death, treatment inefficacy, major protocol deviations, consent withdrawal, lost to follow-up or other reason). Time between baseline and premature withdrawal^{DD} (weeks) will also be presented.

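### LDA and remission percentages at W12 and W24 drop some ITT patients and carry others forward, with no non-responder rate beside them

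*Protocol*

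**What the plan says.** DAS28-ESR and CDAI LDA and remission at W12 and W24 are named secondary endpoints (Protocol 9.2.1.3). SAP 5.2 assigns the secondary analyses to the ITT population. Two rules decide who enters the percentage.

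- **Denominator.** Protocol 11.4.2.2: "Patients with missing data will not be included in the calculation of percentages". SAP 5.3.2.3 states no denominator for these endpoints.
- **Last value.** After treatment discontinuation for lack of efficacy or an adverse event (other than an NSAID adverse event), SAP 6.4 says "the last available endpoint before the considered event will be taken in account". Protocol 11.4.2.1 has the same rule and gives its scope as "for RAID score for primary endpoint and for all other secondary endpoints". SAP 6.4 opens by referring to the primary endpoint but then names the other secondary endpoints too. Everything else is left as missing: "For all other cases, missing data will not be replaced".

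SAP 5.3.1 lists the withdrawal reasons to be tabulated: "adverse event, death, treatment inefficacy, major protocol deviations, consent withdrawal, lost to follow-up or other reason". The last-value rule names only adverse event and lack of efficacy. SAP 3.1 adds a reporting safeguard: "For all the variables, number of available and missing observations will be specified". Neither document plans a non-responder analysis, or any other missing-data sensitivity analysis, for the binary endpoints.

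**The concern.** A percentage labelled ITT will not have the ITT count as its denominator, and some of its responders may be patients who had already stopped treatment. This is a single-arm study, so no control group is subject to the same rules and each percentage will be read on its own.

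The visit windows in SAP 6.6 sharpen the carry-forward point. W12 covers days 77 to 91 and W24 covers days 161 to 175. Take a patient in remission at W12 who stops for lack of efficacy at day 126. The early-withdrawal visit records DAS28-ESR and CDAI (Protocol 10.1.5), but day 126 lies in neither window, and by the logic of the SAP's own example those data are not used. The last value before the event is then the W12 remission, and the patient can be reported as in remission at W24.

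**Working it through.** **The plan's own figures.** The Clinical Trial Summary has 140 included and at least 112 evaluable, "assuming almost 20% of non-evaluable patients": 140 × (1 − 0.20) = 112. With SD 2.5 the 95% half-width is 1.96 × 2.5/√112 = 0.463, below 0.5 as stated. Protocol 11.1 and SAP 1.4 give 122 evaluable instead, which is 122/140 = 87.1%, or 12.9% non-evaluable. All of these figures are planning values for RAID. The documents give no expected missing rate for DAS28-ESR or CDAI and no expected remission rate for this study.

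**Direction against a non-responder rate.** Let N be the ITT count, E the number excluded, R the responders still on treatment with data, and C the responders counted although treatment had stopped.

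- Planned rate = (R + C)/(N − E)
- Non-responder rate = R/N

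Since C ≥ 0 and E ≥ 0, the planned rate is equal or higher. This assumes that both rows use the same value for every patient still on treatment.

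**Size of the denominator rule alone (C = 0).** Let d be the share with missing data and s the share of those kept by the last-value rule. The excluded share is e = d(1 − s) and the factor is 1/(1 − e). Both d and s are assumptions. The plan does not say whether a carried-forward patient counts as evaluable, so s = 0 is included. The count of 30 responders among 112 completers is illustrative.

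| d | s | e | Factor | Example |
|---|---|---|---|---|
| 20% | 0 | 20% | 1/0.80 = 1.25 | 30/112 = 26.8% against 30/140 = 21.4% |
| 20% | 50% | 10% | 1/0.90 = 1.11 | 30/126 = 23.8% against 30/140 = 21.4% |
| 20% | 75% | 5% | 1/0.95 = 1.05 | 30/133 = 22.6% against 30/140 = 21.4% |
| 5% | 50% | 2.5% | 1/0.975 = 1.03 | 26.6% against 26.6% × 0.975 = 25.9%, a gap of 0.7 points |

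The 26.6% in the last row is the W24 DAS28-ESR remission rate on sarilumab in the monotherapy trial quoted in Protocol 4.1.2, used only for illustration. With 122 evaluable and all 18 others excluded, the factor is 140/122 = 1.15.

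**Adding carried-forward responders.** Take the second row, with 14 carried forward and 14 excluded, and suppose 3 of the 14 carried values are in remission. The planned rate is 33/126 = 26.2% against 21.4%, a gap of 4.8 points and a factor of 1.22. Without them the gap is 2.4 points.

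**Direction against the truth.** Take a reported rate of 26.6% with e = 10%, accepting carried values as they stand. If every excluded patient were a non-responder, the ITT rate would be 26.6% × 0.90 = 23.9%. If every one were a responder, it would be 23.9% + 10% = 33.9%. The reported figure lies inside that range.

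**The case against.** A reader might infer that dropouts as a group are removed and that the percentages are therefore inflated by a quarter and describe only patients who stayed. The documents do not support this. Leavers for lack of efficacy or an adverse event, plausibly those least likely to be in remission, stay in numerator and denominator. Entry requires DAS28-ESR above 3.2 at screening, so an early failure carried forward will often count as not in LDA. Compared with observed cases only, the last-value rule can then lower the rate. The 20% is an allowance for RAID, not a forecast for these endpoints, and the documents say nothing about the response of patients lost for other reasons.

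It can also be said that patients are followed after stopping treatment (Protocol 10.3.4), that missing counts and withdrawal reasons are tabulated, and that these are descriptive endpoints with no test or threshold. Non-responder counting has its own downward bias.

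Most of this stands, and it limits both the size of the point and what can be said about its direction. Two gaps remain. Missing counts let a reader rebuild the ITT denominator, but not identify responders counted only through a carried-forward value. The per-protocol repeat does not help either. It is conditional (SAP 5.2) and requires patients to be evaluable for the main criterion (SAP 3.2), so it tends to remove more of the patients in question.

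**Conclusion.** The point holds in a limited form. The LDA and remission percentages exclude ITT patients missing for reasons other than lack of efficacy or an adverse event. They can also count a patient who has stopped treatment as a responder, and no non-responder rate is planned for comparison. Against such a rate the planned one is equal or higher by arithmetic. That it overstates the true rate is possible but not established.

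The factor of 1.25 is the ceiling for the denominator rule at 20% missing, and it requires that none of those patients be carried forward. It is about 1.15 if the 122 evaluable patients of Protocol 11.1 and SAP 1.4 are used, about 1.11 at 20% with half carried forward, and under one percentage point at 5% missing with half carried forward. Carried-forward responders would add to each of these by an amount the documents do not allow one to predict. All of the splits are assumptions. The matter affects secondary descriptive results, not the primary RAID analysis, and is worth correcting because the correction is cheap.

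**What to change.** In Protocol 11.4.2.2 and SAP 5.3.2.3, add a row for DAS28-ESR LDA, DAS28-ESR remission, CDAI LDA and CDAI remission at W12 and W24. It should have all ITT patients in the denominator and count missing or treatment-discontinued patients as not in LDA or remission. Keep the planned rate beside it, and state in SAP 5.3.2.3 the denominator of the planned rate and that the last-value rule applies to these binary endpoints.

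The cost is one extra row in four tables, with no new data and no design change. The downside is that the added rate is conservative and will look no better, and usually less favourable, than the planned one.
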